## 4 STUDY DESIGN

### 4.1 Overall design

This is a randomised, controlled, double-blinded feasibility study. The intervention is randomisation to one of two treatment arms:

- Placebo
- Vitamin C 500mg

Patients and clinicians will be blinded to their intervention arm until the end of the study. Medication will be dispensed in boxes of exact same shape, size and colour. The treatment period will be for fifty days with a six-month follow up.

The trial will be conducted at five sites in Bayside Melbourne:

- Frankston public hospital
- Frankston private hospital
- Beleura Private Hospital
- Holmesglen Private Hospital
- Cabrini Brighton Private Hospital

### 4.2 Justification for dose

Patients will receive an oral dose of vitamin C or placebo. Patients will receive an identical box with either placebo or 500mg.

In Australia, vitamin C is usually dispensed in 250mg, 500mg or 1000mg capsules. 500mg dosing was selected as previous studies have not demonstrated any complication in patients taking 500mg vitamin C. It has been demonstrated that 250mg is less effective compared to 500mg dosing in the prevention of CRPS(2). There has also been a very small complication rate in dosing greater than 1000mg/day(18). Therefore 500mg was determined as most appropriate for this feasibility study.

### 4.3 Trial population

Patients aged 18 and over will be eligible for the trial. Patients undergoing elective or emergency foot and ankle surgery and the five sites will be invited to participate.

Patients who are unable to provide informed consent to participate in the trial will be excluded.

### 4.4 Eligibility criteria

Participants will be assigned to a randomised trial treatment only if they meet all of the inclusion criteria and none of the exclusion criteria.

---

#### 4.4.1 Inclusion criteria

Each patient needs to meet the following criteria to be eligible to participate in the trial:

- Patients need to be aged 18 and over to participate in the trial. This is because most fractures in the lower limb in children are treated non-operatively. In addition, most sites have limited numbers of younger patients who have surgery for foot or ankle problems, recruitment of people under the age of 18 is unfeasible.
- Patients need to be able to provide informed consent for the trial via a signed and dated consent form. Patients who are unable to provide informed consent because of (for example) cognitive impairment will be excluded.
- Patients who present to Peninsula Health, Frankston Private Hospital, Holmesglen Private Hospital, Beleura Private Hospital or Cabrini Brighton Private Hospital for surgery of the foot and ankle, either elective or emergency, will be eligible to participate.

#### 4.4.2 Exclusion criteria

Patients meeting the following criteria will be excluded from the trial:

- Current or recent (ie less than three months prior to randomization) use of vitamin C, either as an isolated substance or as part of a multi-vitamin tablet. This is because the vitamin C dosing will not be standardized if patients are also taking the vitamin, and there is potential for overdosing. Vitamin C has a half-life of 10-20 days and therefore a long exclusion period is required.
- Patients who are pregnant or breastfeeding will be excluded due to the unknown safety risks in this patient population.
- Patients who are unable to commence taking the placebo/vitamin C medication within 72 hours after their surgery will be excluded from the trial
- Patients unable or unwilling to take oral medications.
- Patients who are vegan (as the placebo acidophilus is dairy based)

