## 2.3. Risk/Benefit assessment

### 2.3.1. Known potential risks

Trauma is known to increase vitamin C requirements. However, in patients exceeding 1000mg of vitamin C daily the multivariate relative risk of kidney stone formation in men was 41% higher than in those consuming 90mg a day. Vitamin C in high doses (in excess of 5000mg a day) has been suggested to cause haemolysis in glucose-6-phosphatase dehydrogenase deficient patients, which has a high prevalence rate amongst persons of

---

African, Asian or Mediterranean descents(15). Neither Zollinger nor Besse described any complications from their vitamin C dosing (maximum 1000mg) in their published trials (2)(3).

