#### **4.7 Recruitment and identification of potential participants**

Patients will be recruited in the following ways:

- Following HREC approval, elective and trauma theatre lists will be screened and potential patients with elective and trauma foot and ankle surgery will be identified and asked to participate in the trial. They will then be contacted by a member of the research team.
- A poster advertising the trial will be available in fracture clinic and elective orthopaedic clinic and patients will have an opportunity to discuss participating in the trial directly with their treating clinician who will then pass on the details to a member of the research team.
- Clinicians in the fracture and elective clinics will invite eligible patients to participate in the trial.

Contact details for the patients, including an email address and mobile phone number, will be passed on to a member of the research team for contact as well as access to the electronic medical record for patient contact information.

The target trial population is all patients aged 18 and over who present for elective or trauma surgery of the foot and ankle. For this feasibility study, it is estimated that approximately 100 patients will need to be enrolled to assess the feasibility of the trial.

The recruitment period will be six months.

Recruitment will be done at the following sites:

- Peninsula Health – Frankston Hospital
- South East Orthopaedic Surgery – Frankston Private Hospital, Beleura Private Hospital, Holmesglen Private Hospital, Cabrini Brighton Private Hospital

Recruitment will most commonly occur in the outpatient setting. For patients presenting with trauma-related conditions, recruitment may occur in the inpatient setting.

Prior to performing any trial-specific intervention, a signed consent form will be obtained for each participant. The process will be that the investigator or delegated member of the trial team will discuss the trial with the potential participant. The investigator will provide the Participant Information and Consent Form to the patient. This document will describe the purpose of the trial, the procedures to be followed, and the risks and benefits of participation.

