The investigator will conduct the informed consent discussion and will check that the participant comprehends the information provided. The investigator will answer any questions about the trial. The patient will be invited to provide written consent. Consent will be voluntary and free from coercion. The investigator who conducted the consent discussion will also sign the informed consent form. A copy of the consent form will be given to the participant where the participant has signed.

---

It will be documented in the participant's record that consent has been provided. When the all the inclusion/exclusion criteria have been addressed and the eligibility of the participant confirmed, the participant may be assigned to a trial arm/intervention.

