### 5.2.1 Description of trial investigational products

#### 5.2.1.1 Placebo

---

Active substance	Lactobacillus acidophilus and Bifidoobacterium animalis
Trade or Generic name	Blackmores Acidophilus
Dosage form	Capsule
Route of administration	Oral one capsule daily for fifty days

---

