#### 5.2.1.1 Vitamin C 500mg

---

Active substance	Ascorbic Acid (Vitamin C) 500mg Citrus bioflavonoids extract 50mg
Trade or Generic name	Amplio Vitamin C
Dosage form	Capsule
Route of administration	Oral one capsule daily for fifty days

---

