### 7.4 Description of procedures

All members of the orthopaedic team involved in assessing post-operative patients undergo an education session about the project and how to assess for CRPS. CRPS is a relatively common diagnosis that doctors of all grades should confidently be able to detect although the importance of documentation according to our diagnostic criteria will be made during the briefing. The briefing will be repeated during each rotation as the junior doctors rotate through different terms.

To determine suitability for inclusion, all elective and trauma orthopaedic theatre lists will be screened to determine patient eligibility and enrol participants. Adult patients identified as undergoing foot and ankle elective or trauma surgery, as defined as any procedure at or below the level of the distal one third of the tibia, will be deemed a potential participant. Patients will be contacted by a researcher prior to their surgery via telephone or email. If patients were admitted as an inpatient, seen in an outpatient clinic or after hours, they will be contacted by a researcher within 72 hours following their surgery. They will be

---

randomised and commenced on their treatment within 72 hours of injury or surgery. If patients are unable to commence their vitamin C/placebo treatment within 72 hours of injury or surgery they will be deemed ineligible to participate as comparative studies have commenced vitamin C supplementation the following day after surgery or injury.

If patients consented to their own surgical procedure, they will be deemed of sound mind to consent to the trial as well. Patients will be asked specifically the following questions:

- Have you taken vitamin C or any other multivitamin supplementation that contains vitamin C, in the last three months? If they answer yes, or are unsure they will be deemed ineligible to participate.
- What date and time was your surgery? If this was greater than 72 hours prior to randomisation and commencement of treatment they will be deemed ineligible.
- Are you pregnant or breastfeeding?

The following information will be collected during the initial contact with the patient should the patient consent to participation in the trial:

- Patient identifiers:
  - Age
  - Sex
  - First name/last name
  - Email address
  - Contact phone number.
- Patient demographics
  - Date of birth
  - Sex
  - Previous history of CRPS
  - Previous history of mental health condition

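### Vegans are excluded because the placebo contains dairy, but patients with a known milk allergy or an allergy to another capsule ingredient are not.

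*Protocol*

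**What the plan says.** Protocol section 4.4.2 has five exclusions: recent vitamin C use, pregnancy or breastfeeding, inability to start treatment within 72 hours, inability or unwillingness to take medicines by mouth, and veganism. The last is worded "Patients who are vegan (as the placebo acidophilus is dairy based".

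Section 4.4 says participants are assigned treatment "only if they meet all of the inclusion criteria and none of the exclusion criteria". Section 4.7 adds that once eligibility is confirmed "the participant may be assigned to a trial arm/intervention".

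Section 5.2.1.1 names the placebo product as "Blackmores Acidophilus", a two-strain probiotic capsule, without giving its milk-protein or lactose content. The entry for the active product lists "Citrus bioflavonoids extract 50mg" besides the ascorbic acid. Both are taken once daily for 50 days.

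In section 7.4 the screening script begins "Patients will be asked specifically the following questions". Three questions follow, on vitamin C use, timing of surgery, and pregnancy or breastfeeding. The risk section (2.3.1) begins "Trauma is known to increase vitamin C requirements" and deals with vitamin C throughout. Of the participant information form, section 4.7 says "This document will describe the purpose of the trial, the procedures to be followed, and the risks and benefits of participation". That form is not among the pages available for this review.

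**The concern.** The stated reason for the vegan exclusion supports a wider rule than the one written. If dairy content is reason enough to exclude someone on dietary grounds, it is a stronger reason to exclude someone for whom milk is a medical hazard. The criteria do the first and not the second.

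Blinding makes a written rule more important. Under section 5.2 the boxes carry only a randomisation number, and the other labelling follows the vitamin C packet. The four label items listed there include no dairy statement. An allergic patient allocated placebo cannot count on the label for a warning, so the check has to come before randomisation. At stake is an avoidable exposure of participants. The validity of the analysis is not in question.

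**Working it through.** The protocol gives no figure to reproduce on this point. The check has two parts.

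**1. Does any other section close the gap?**

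| Protocol section | What it offers | Covers milk or ingredient allergy? |
|---|---|---|
| 4.4.1 Inclusion | Age, consent, surgery at a listed site | No |
| 4.4.2 Exclusion | Five items as above | Vegans only |
| 4.6 Screen failures | Patient contact, medical records, operating lists and referrals as information sources | Names sources; no instruction to act on an allergy |
| 7.4 screening questions | Three questions | No |
| 2.3.1 to 2.3.3 Risks and benefits | Vitamin C | Placebo dairy content not mentioned |
| 5.2.7 and 5.2.8 Excluded and concomitant treatment | Vitamin C supplements, drug interactions, chemotherapy | No |
| 5.2.9 Discontinuation | Refers back to the exclusion criteria; stopping for intolerable events | Not before exposure |

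The section 7.4 questions are not the whole eligibility check, since they also leave out vegan status. Even so, no other section states an allergy check. The active capsule's citrus extract has no hypersensitivity criterion either.

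**2. How many people might be exposed?**

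Inputs:
- Placebo participants: 50 (section 11.1, at least 50 per arm).
- Share p of enrolled adults with known milk allergy: not in the protocol. Assumed 0.1%, 0.5% and 1%.
- Nobody is screened out by discretion or by their own refusal.

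Formulas: expected number on placebo = 50p; chance of at least one = 1 − (1 − p)^50; recruits lost per 100 if excluded = 100p.

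| Assumed p | Expected on placebo | Chance of at least one | Recruits lost per 100 |
|---|---|---|---|
| 0.001 | 0.05 | 1 − 0.999^50 = 0.049 | 0.1 |
| 0.005 | 0.25 | 1 − 0.995^50 = 0.222 | 0.5 |
| 0.01 | 0.5 | 1 − 0.99^50 = 0.395 | 1.0 |

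These figures count people exposed, not reactions. Fifty capsules per person is a ceiling, since a participant who reacts can be stopped under section 5.2.9.

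**The case against.** The best case for leaving the text alone is that other safeguards would probably catch an allergic patient.

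- **Oral medication.** Someone who says they cannot or will not swallow a dairy capsule might be held to meet the exclusion about taking medicines by mouth. That criterion concerns oral medication in general, however. If it covered objections to this particular capsule, the vegan criterion would not be needed. It also prompts nobody to disclose an allergy.
- **Records.** Section 4.6 allows eligibility information to come from medical records. That is a chance to notice an allergy, but no criterion tells staff what to do with it.
- **Discretion and consent.** The criteria are a necessary condition, and section 4.7 permits assignment without requiring it, so an investigator may decline to enrol. The unseen consent form may disclose the dairy content. Both points stand. But discretion works only if the allergy comes to light, and disclosure works only if the patient makes the connection. The plan did not leave vegans to either.
- **Later safeguards.** Side effects are asked about at each review, treatment can be stopped, and there is an independent safety monitor. All of these act after exposure.
- **Size.** The hazard at this dose cannot be established from the protocol, and the exposure figures rest on assumed shares. That is correct, and it limits how much weight the point can bear.
- **Citrus extract.** The protocol identifies no concern with this ingredient. It only supports wording the new criterion to cover both capsules.

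**Conclusion.** The concern holds. The eligibility section is shown in full, and its dairy rule is narrower than its own rationale. A patient with a known milk allergy who is not vegan is eligible as written, and prevention rests on individual judgement or on the patient declining, across five sites. The absence of a stated rule is certain from the text. Whether an allergic patient would in fact be dosed is not, because that depends on the unseen consent form, on local screening and on the product's composition.

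The probability of exposing at least one such patient runs from 5% to 39% over the assumed range, with no screening out. The probability of harm cannot be given. No effect on the feasibility outcomes or the CRPS comparison is claimed. This should be corrected because it protects participants at almost no cost, not because it threatens the results.

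**What to change.** In section 4.4.2, keep the vegan criterion and add: *Known milk (dairy) allergy, or known hypersensitivity to any ingredient of either capsule.* Add a matching question to the screening list in section 7.4. These two changes are what matter. It would also help to add a sentence to section 2.3.1 stating that the placebo contains dairy.

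Do not add a general exclusion for dairy intolerance, which would turn away more patients than the allergy concern calls for. The dose-modification rule (5.2.3) and the unblinding rule (6.3.1) can stay as they are.

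The cost is one line, one question and one optional sentence. Recruitment is itself a feasibility outcome (section 3.2), so lost recruits count: 0.1 to 1 per 100 for milk allergy under the assumed shares, plus an unknown but small number for other ingredients.

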#### 4.5 Lifestyle considerations

Patients will be required to take one capsule once per day for fifty days. It is not expected this will inconvenience patients and compliance in other trials has been excellent.

#### 4.6 Screen failures

Eligibility information will be obtained:

- Via the patient themselves – contacting the researcher/s directly
- Via the medical records, operating lists and referral screening after approval from the Human Research Ethics Committee

Patients will then have their willingness to participate recorded in the electronic medical record.

---

Those who are found, during the screening procedures, to be ineligible for trial inclusion are termed “Screen failures and they are not assigned to the intervention / are not randomised” and will be ineligible to continue in the trial.

#### **4.7 Recruitment and identification of potential participants**

Patients will be recruited in the following ways:

- Following HREC approval, elective and trauma theatre lists will be screened and potential patients with elective and trauma foot and ankle surgery will be identified and asked to participate in the trial. They will then be contacted by a member of the research team.
- A poster advertising the trial will be available in fracture clinic and elective orthopaedic clinic and patients will have an opportunity to discuss participating in the trial directly with their treating clinician who will then pass on the details to a member of the research team.
- Clinicians in the fracture and elective clinics will invite eligible patients to participate in the trial.

Contact details for the patients, including an email address and mobile phone number, will be passed on to a member of the research team for contact as well as access to the electronic medical record for patient contact information.

The target trial population is all patients aged 18 and over who present for elective or trauma surgery of the foot and ankle. For this feasibility study, it is estimated that approximately 100 patients will need to be enrolled to assess the feasibility of the trial.

The recruitment period will be six months.

Recruitment will be done at the following sites:

- Peninsula Health – Frankston Hospital
- South East Orthopaedic Surgery – Frankston Private Hospital, Beleura Private Hospital, Holmesglen Private Hospital, Cabrini Brighton Private Hospital

Recruitment will most commonly occur in the outpatient setting. For patients presenting with trauma-related conditions, recruitment may occur in the inpatient setting.

Prior to performing any trial-specific intervention, a signed consent form will be obtained for each participant. The process will be that the investigator or delegated member of the trial team will discuss the trial with the potential participant. The investigator will provide the Participant Information and Consent Form to the patient. This document will describe the purpose of the trial, the procedures to be followed, and the risks and benefits of participation.

The investigator will conduct the informed consent discussion and will check that the participant comprehends the information provided. The investigator will answer any questions about the trial. The patient will be invited to provide written consent. Consent will be voluntary and free from coercion. The investigator who conducted the consent discussion will also sign the informed consent form. A copy of the consent form will be given to the participant where the participant has signed.

---

It will be documented in the participant's record that consent has been provided. When the all the inclusion/exclusion criteria have been addressed and the eligibility of the participant confirmed, the participant may be assigned to a trial arm/intervention.

#### **4.8 Consent**

Patients will be contacted by a member of the research team prior to participating in the trial or receiving any intervention once detected as being eligible for the trial.

The following conditions will be met for each patient:

- Disclosure of relevant information to prospective research participants
- Comprehension of the information provided
- Voluntary agreement of the participant, free from coercion

Prospective patients will receive written and verbal information about the trial, the risks involved and the follow up required for the study.

Consent from minors will not be sought as only patients aged 18 and over are eligible for the trial. A member of the research team will obtain informed consent. Patients will verbally consent to participating in the trial and this will be confirmed in writing and also documented in the patient's Electronic Medical Record.

If patients are deemed ineligible for participation, or decline to participate, they will be recorded anonymously with reason as to why they did not participate in the trial.

Recruitment and consent may be performed by the investigators as well as other members of the investigative team. Patients will be given opportunity to consider their involvement in the study, and to discuss their involvement with family members or support persons. It will be made clear that participation is voluntary, and the patient's decision to participate will not affect their relationship with any of the treating practitioners including [name]. It will be made clear that should patients choose not to participate in the study, their surgery and/or follow up will not be adversely affected and will not differ from those who chose to participate in the study.

### **5 INTERVENTION**

#### **5.1 Treatment arms**

There will be two treatment arms: placebo and vitamin C 500mg. Patients will be randomised to one of the two arms.

#### **5.2 Trial Intervention(s)**

Placebo and Vitamin C 500mg capsules will be sourced from Peninsula Health pharmacy and kept in a locked office in all sites. Boxes will be labelled with a randomised number only.

Pharmacy will have access to the randomised number and its allocation to placebo or vitamin C 500mg. The patient, clinicians and researchers will not be privy to the randomised group.

Other labelling of the intervention will be as applicable on the vitamin C packet. This includes:

- Expiry date
- For clinical trial use only
- Keep out of reach of children
- Store in a cool, dry place

---

Placebo and both vitamin C doses will be of similar size and taste. Patients will take one capsule orally once per day for fifty days. Capsules are stored in a cool, dry place and prepared by pharmacy.

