### 5.2.9 Discontinuation from trial intervention

Participants who discontinue trial treatment will remain in the trial. The remaining trial procedures should be completed as indicated by the trial protocol.

Participants may discontinue trial treatment for the following reasons:

- Participant / legal guardian request to discontinue trial intervention
- Investigator decision to discontinue a participant from the trial intervention if the participant:
  - Is pregnant
  - Experiences a serious or intolerable adverse event such that continued trial intervention would not be in the best interest of the participant
  - Develops, during the course of the trial, symptoms or conditions listed in the exclusion criteria
  - Requires a medication that is prohibited by the protocol
  - Requires early discontinuation for any other reason

The investigator may also withdraw all trial participants from the trial treatment if the trial is terminated.

The procedure for transitioning a participant off the trial drug and/or onto alternate therapy is as follows: patients will be advised to cease taking the medication immediately and return the unused medication to the researcher.

For the safety of all participants ceasing trial treatment, the protocol-specified safety evaluations should be undertaken to capture new safety events and to assess existing, unresolved safety events. All scheduled follow-ups of trial participants should also occur following treatment discontinuation, where possible.

In addition to the safety evaluations, the data to be collected at the time of trial intervention discontinuation will include the following:

- Reason for discontinuing medication
- Any adverse effects
- Involvement of other practitioners in treatment of adverse events

A dedicated Case Report Form (CRF) page will capture the date and the specific underlying reason for discontinuation of the trial intervention.

The participant should remain in the trial for scheduled visits for trial assessments (follow-up) per protocol.

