### 6.3 Breaking of the trial blind

#### 6.3.1 On trial

The randomisation code for an individual participant may only be unblinded in emergency situations, where the Investigator decides a participant cannot be adequately treated without knowing the identity of their treatment allocation. Specifically, if the patient reports symptoms of vitamin C toxicity such as severe gastrointestinal upset or kidney stones, the randomisation code will be broken in order to communicate to the patient's treating physician(s) the vitamin C dosing. To break the randomisation code the Investigator must open the emergency unblinding envelopes provided, or contact the randomisation

---

facility/personnel. If any unblinding envelope is opened, the time, date, participant number and reason for opening must be documented.

Blinding is imperative in this trial to avoid bias and answer the specific research question and all researchers are aware of the importance of this.

It is not expected that inadvertent unblinding will occur due to strict randomisation and blinding protocols.

[figure not shown]

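### Exact masking is promised only for the box: the two capsules are not required to look alike, and unused capsules can reach staff who rate CRPS

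*Protocol*

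**What the plan says.** **The claim.** Section 4.1 states: "Patients and clinicians will be blinded to their intervention arm until the end of the study". Section 6.3.1 calls blinding essential to avoiding bias and adds: "It is not expected that inadvertent unblinding will occur due to strict randomisation and blinding protocols".

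**The box.** Section 4.1 says: "Medication will be dispensed in boxes of exact same shape, size and colour". Section 4.2 repeats the point: "Patients will receive an identical box with either placebo or 500mg".

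**The capsules.** Section 5.2 says: "Placebo and both vitamin C doses will be of similar size and taste". It also says that pharmacy prepares the capsules, without describing what the preparation involves. Section 5.2.1 names the placebo as "Blackmores Acidophilus" and the active product as a different brand, containing 500 mg ascorbic acid and 50 mg citrus bioflavonoids.

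**Returns.** Section 5.2.9 tells participants who discontinue treatment to "return the unused medication to the researcher". Section 5.2.5 asks for leftover capsules back at the end of the fifty days but does not say who receives them. It makes the trial team responsible for settling discrepancies in the drug count.

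**Outcome rating.** Section 7.4 has CRPS examined by a research team member or the treating clinician, and later in the same section gives the follow-up history and examination to the study researchers.

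**The concern.** A double-blind claim depends on what participants and assessors actually see. A participant handles the capsules daily for fifty days, and an assessor may be handed what is left. Matching the box protects only until it is opened.

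CRPS is exposed to any leak. The Budapest criteria combine reported symptoms, clinician-observed signs, a judgement that pain is disproportionate to the event, and a judgement that no other diagnosis fits better. Each can shift if the participant or the rater knows or suspects the arm. With only two arms, a rater who has learned which capsule is which would know the arm of every participant whose capsules they see.

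The CRPS comparison is a secondary objective here, but suitability of the intervention is part of the primary feasibility objective. A later definitive trial would probably inherit the same products and return route.

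**Working it through.** No figure in the protocol bears on this point, so the check sets its provisions side by side.

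**1. What must match.**

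| Item | Requirement | Section |
|---|---|---|
| Box: shape, size, colour | Exact match | 4.1, 4.2 |
| Capsule: size, taste | Similar | 5.2 |
| Capsule: colour, shape, markings, smell | None stated | – |
| Source product | Two different brands | 5.2.1 |

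The capsule standard is weaker than the box standard and leaves out most of what an observer would notice. Its sentence also refers to two vitamin C doses, while sections 4.1 and 5.1 have one active arm. The only sentence on capsule masking was therefore not brought into line with the present design.

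**2. Who can see the capsules.** For participants who discontinue, the researcher is the named recipient. For day-50 leftovers the recipient is open. Treatment starts within 72 hours of surgery, so the fifty days end at most about 50 + 3 = 53 days after surgery, and 53 / 7 = 7.6 weeks. That falls between the review at five to six weeks and the next one, which section 3.2 places at 10–12 weeks and the synopsis at eleven to fourteen. No visit is tied to the end of treatment. If leftovers are brought to the next scheduled contact, they arrive at a CRPS assessment. That last step is an inference; the protocol does not state it.

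**3. Whether the same people rate CRPS.** Section 7.4 allows research team members to do so and, in a second statement, assigns the examination to study researchers. No provision separates those who receive capsules from those who rate the outcome. Overlap is allowed, though not certain.

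**4. What follows.** For an assessor to be unblinded by this route, four things must all happen:

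- capsules are returned;
- the recipient also rates CRPS;
- the recipient looks at the capsules;
- the two products can be told apart.

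The protocol provides for the first, permits the second and does nothing to prevent the third. On the fourth it is silent.

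**The case against.** **The capsules may look the same.** Nothing in the protocol says they differ. Pharmacy prepares them, and that could include masking. Section 5.2 says researchers will not know the allocation, and the table in section 6.2 lists clinicians assessing outcomes among those kept unaware. All of this stands. A reader might infer from the two brand names that the blind is already broken, but the text does not support that. It supports only that indistinguishable appearance is not required.

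**The return route is narrow.** Return to the researcher is explicit only for discontinuers, and section 5.2.5 hopes there will be no leftovers. This also stands and limits how many participants are affected. It does not explain why the recipient should be someone who may rate CRPS when a pharmacist is available.

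**The vegan exclusion.** Section 4.4.2 excludes vegans because the placebo is dairy-based, and a reader might infer that screening gives the allocation away. It does not. At most it discloses what the placebo contains, not who receives it, and the screening questions listed in section 7.4 do not include one on veganism.

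**No check of blinding is planned.** A reader might call this an error. Asking for treatment guesses is optional practice, and guesses can reflect symptoms or side effects as much as failed masking. Its absence is not a fault in the protocol.

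**A related conflict.** The second section numbered 5.2.1, on discontinuation of treatment, has the randomisation envelope opened when treatment stops, while section 6.3.1 restricts unblinding to emergencies. Those passages must be reconciled. The present point does not depend on how that is done.

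**Conclusion.** The point holds as a gap in the specification. The protocol secures the box, does not require the capsules to be indistinguishable, and lets unused capsules reach people who may rate a partly subjective outcome. Its confidence about inadvertent unblinding is therefore not backed by its own provisions for capsules and returns.

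The size cannot be calculated. If the products look alike, the return route does no harm. If they differ visibly, the assessor's blind is at risk for each participant whose capsules a rater sees. The documents give neither the appearance of the capsules nor an expected number of returns, so any stated bias in the CRPS comparison would rest on invented inputs.

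The conclusion assumes only that the researcher in section 5.2.9 may be among the study researchers who examine participants under section 7.4. The text permits this and nowhere excludes it. The matter is modest, but worth correcting because the main change is nearly free.

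**What to change.** 1. **Returns (sections 5.2.9 and 5.2.5).** Require all unused capsules, whether from discontinuation or left over at day 50, to go back in the closed box to the trial pharmacist and never to anyone who rates CRPS. The pharmacist already holds the allocation and keeps the drug records, and can pass on counts alone for reconciliation. The cost is a wording change plus the logistics of getting boxes from the private sites to the pharmacy at Peninsula Health.

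2. **Capsules (section 5.2).** Replace the outdated sentence about two vitamin C doses, either with a requirement that the two capsules be indistinguishable in appearance, saying how pharmacy achieves this, or with a plain statement that only the box is matched, limiting the double-blind claim accordingly. The second option is wording only. The first costs little if the products already look alike. If they must be put into a common shell, the work is about 100 participants (section 4.7) × 50 capsules = 5,000 capsules, which is not trivial.

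3. **Optional.** A treatment-guess item for participant and assessor could be reported under suitability of the intervention. It would have to be collected at a visit, so the decision belongs before recruitment, but the fix does not depend on it.
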